Appendix 1: Participant Baseline Questionnaire (Part-Quest-baseline)

1. Is this your first consultation with your general practitioner concerning your current musculoskeletal pain condition? Mark one answer.

Yes No, this is consultation number _____ with my current musculoskeletal pain condition

[figure not shown]
2. Draw a circle around the stage of your current physical features. Girls draw on the right figure and boys on the left.

3. How tall are you? _____ cm

4. How much do you weigh? _____ kg

Below is a drawing of **your** body.

5. Draw on your body the areas you have had pain or it has hurt, during the past two weeks. If you haven't felt hurt or pain during the past two weeks or currently, please write X here _____ (50)

6. Have you felt hurt during the past two weeks leading to not being able to participate in play in the school yard or sparetime activities (ex. football or other sparetime activity)? yes _____ no _____

7. Draw a circle around the area of your body, where you have had the **most** problems with pain. You may only draw **one** circle.

8. Mark the statements below, that are true about your pain. You may mark more than one.

[figure not shown]
- it can easily be ignored
- it affects my concentration
- sometimes I have to take pain medication
- sometimes I can't attend school because of the pain.

If you are 8 to 11 years old, please answer question 9.

If you are 12 to 19 years old, please *skip* question 9 and answer question 10.

9. These faces show how much something can hurt.

This face shows no pain.

The faces show more and more pain up to this one – it shows very much pain. Circle the face that shows how much you hurt (46).

10. On a scale of 0 to 10, where 0 is no pain and 10 is the worst possible pain, circle the number that best represents your pain (9).

0 1 2 3 4 5 6 7 8 9 10

Your name _____ Your phone no. _____ Your e-mail _____ 13

Appendix 1: Participant Baseline Questionnaire (Part-Quest-baseline)

11. How long have you had your current pain? (50) _____
12. What is the cause for your current MSK pain (ex. a fall, a hit or other)? (If you are familiar with it) (50) _____
13. How long does a pain episode usually last (40)?
 Less than 3 hours
 Less than 24h
 1-7 days
 More than 7 days
14. How often do you have a pain episode?(51)
 At least once a week
 Less than once a week
15. How often do you feel nervous?(52)
 Often/sometimes Seldom/never
16. Which zipcode(s) do you live in? _____
17. If not born in Denmark, in which country were you born and how long have you lived in Denmark?
 Country of birth _____ Months/years lived in Denmark _____
18. What do you feel the most as? (53) Please answer this question, no matter country of birth.
 Danish
 Danish with foreign background
 Foreigner
 I don't know
19. How large a part of your friends have immigrant background/not born in Denmark? (53) Mark one.
 None Almost none Almost all All
20. Outside school hours, how many hours a day do you spend watching TV/tablet/mobile phone/computer or do other activities when mostly sitting down(39)? _____ hours/day
- 
-  19. How much do you sleep on average per night(43)?
 7 hours or less
 8-10h
 More than 10 hours
21. Are you physical active besides school hours? (10) 
 Yes
If yes, how many times per week are you physical active besides mandatory physical education during school hours? _____
 No
22. How often do you drink alcohol? (39, 54)
 More than once a month
 Approximately once a month
 Less than once a month
 I have only had alcohol one time
 I have never had alcohol
23. Do you smoke cigarettes(55)?
 Yes, less than 1 a day
 Yes, 1-4 a day
 Yes, 5-9 a day
 Yes, more than 9 a day
 No, I don't smoke cigarettes
24. How many siblings (including non-biological) do you have? _____
–What number are you in your group of siblings? _____
- 

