At present we lack age-specific prognostic factors in adolescents with MSK pain, although multiple prognostic factors have been identified in adult MSK pain. One systematic review found that higher pain severity upon presentation to the GP, longer pain duration, multiple-site pain, anxiety and/or depression, higher somatic perceptions and/or distress, low social support, higher baseline disability, and greater movement restriction were all associated with a poor prognosis(19). Systematic reviews on adult knee pain suggest an association between low/middle education level, non-skeletal comorbidity, duration of knee symptoms of > 3 months, bilateral knee symptoms, self-reported warm knee, history of non-traumatic knee symptoms, valgus alignment and an unfavorable prognosis(20). Similar to findings in patients with adult low back pain, there was high evidence that fear-avoidance beliefs and meagre social support at work were associated with an poor prognosis(21).

According to Smith et al. there is a statistically significant association between parental pain acceptance on child functional disability, which can be mediated by parent protective behavior and child pain acceptance(22). We also know from previous research that parents' emotional, cognitive, and behavioral responses are highly influential upon children's pain and functional outcomes(23-25). What valuable information can we extract from the parents of children and adolescents with MSK pain at follow-up? These statements highlight the importance of inclusion of parent characteristics including parent pain acceptance when investigating prognostic factors.

If future studies are to tailor and target treatment for the adolescents with the highest risk of long-standing MSK pain, there is a need to identify prognostic factors for an unfavorable prognosis. The aim of this prospective cohort study is to identify the most important prognostic factors for adolescents with MSK pain in general practice.

Framing a research question

To help frame our research question, and re-evaluate its strength and feasibility, we used the PEO approach (Population, Exposure, and Outcome) in conjunction with the FINER criteria (Feasible, Interesting, Novel, Ethical, and Relevant) (26, 27).

PEO

P	Population	Children, adolescents, youth, kids, young adults, teenagers
E	Exposure	Prognostic factors, prognosis
O	Outcome of interest	MSK pain at follow-up

This leads to the **objective** of our study:

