(NVK) National Scientific Ethics Committee

Figure 1 Illustration of the timing of our study up to the point of publication and sharing of results.

Study setting

General practice clinics in Denmark.

Eligibility criteria for participation of participants and parents

Participants

The children and adolescents must have self-reported MSK pain at the time of recruitment and consult the GP in relation to their MSK pain. The primary reason for consultation may not necessarily be listed as MSK pain, but to be eligible for inclusion, MSK pain must be mentioned during the consultation with the GP. We do not have a pre-defined minimum or maximum MSK pain duration as a eligibility criteria and patients are eligible whether or not they have previously consulted their GP for their current MSK complaint.

We define MSK pain according to the International Association for the Study of Pain, IASP as: “pain arisen from muscle, tendon, bone, and joint”. Pain due to tumor, fracture, infection, or systemic and neurological cause will be excluded. Types of pain will be labelled according to the region affected, e.g. back pain, neck pain, shoulder pain, knee pain etc(33).

After consulting the GP in relation to MSK pain, inclusion and exclusion criteria will be applied as follows:

Inclusion criteria:

- 8 to 19 years
- Self-reported musculoskeletal pain

Traumatic pain caused by soft tissue damage, contusion or otherwise (excluding fracture), will be included.

Exclusion criteria:

- 0-7 or 20+ years
- Self-reported musculoskeletal pain due to tumor, fracture, infection, or systemic and neurological causes.

The inclusion and exclusion criteria will be determined at the following time-points:

1. During screening of the time schedule at the GP clinic
2. During the consultation with the GP
3. During a phone call made by the research assistant to either the participant or her/his parent, after retrieving their completed questionnaire from the GP clinic.

Parents

Parental participation will only be eligible after inclusion of their child. If a child is not eligible, or parental consent is not acquired on behalf of the child or adolescent <15 years of age, the parent will not be eligible for inclusion.

Declarations of consent

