With our primary outcome we aim to capture pain that interferes with their everyday lives and collect the location of pain. The patient characteristics (exposures) are based on results from our systematic review(14), used in other studies (when including references).

The specific wording in the outcomes and throughout the questionnaire has been pilot tested among similar aged kids and adolescents.

Our secondary outcomes highlight the development or potential aggravated psychological and social factors related to musculoskeletal pain at follow-up.

Primary outcome

1) MSK pain influence

Q: Have you experienced pain in the past two weeks that have lead you to not being able to participate in play in the school yard or sparetime activities (ex. football or other sparetime activity)(38)?

If yes, we ask them to draw the area where they have experienced this pain with the following question:

Q: Draw on your body the areas you have had pain during the past two weeks (39).

These two questions will form our primary outcome and will be collected at all endpoints.

Secondary outcomes

1) Problemfilled MSK pain.

*Q: Draw a circle around the area of your body, where you have had the **most** problems with pain. You may only draw **one** circle.*

2) Pain intensity depicted on Faces Pain Scale Revised (FPS-R) or a 10 cm VAS scale for 8-11 and 12-19 year olds respectively (9).

Exposures

3) Self-reported anxiety.

Q: "Do you feel anxious"?

4) Self-reported depression (16).

Q: "Do you feel depressed"?

5) Self-reported low self-esteem (16).

Q: "Do you think that you have low self-esteem"?

6) Duration of troublesome pain episode (40, 41).

Q: "How long does a pain episode usually last"? (see appendix 1 and 2 for the Q in full length).

7) Frequency of troublesome pain episode (10, 42, 43).

Q: "How often do have a pain episode"? (see appendix 1 and 2 for the Q in full length).

8) Nervousness (41).

Q: "How often do you feel nervous"? (see appendix 1 and 2 for the Q in full length).

9) Higher disability index (12, 44).

Q's with yes/no answers:

1. is it difficult to fall asleep because of pain?

2. is it difficult to sit during a lesson?

3. does your pain disturb a walk longer than 1km?

4. does your pain disturb your physical exercise?

5. does your pain disturb your hobbies?

10) Higher HFAQ level (40).

Q: "Does your pain make any of the following activities difficult"?

1. reaching up to get a book from a high shelf

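### Baseline items 13 and 14 presuppose recurrent pain episodes and have no answer for a first or continuous pain, and time since onset is collected without a unit

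*Protocol*

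**What the plan says.** In the Exposures list, item 6 is "Duration of troublesome pain episode" and item 7 is the frequency of such episodes, worded "How often do have a pain episode". Appendix 1 measures them with two closed questions.

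- **Item 13** ("How long does a pain episode usually last") offers under 3 hours, under 24 hours, 1 to 7 days, and over 7 days.
- **Item 14** (frequency) offers two answers: weekly or more often, and less than weekly.

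Neither has a box for a first, single or continuous pain. The follow-up form (Appendix 2, item 13) repeats the frequency question and adds a third answer, for pain that never lets up.

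The eligibility section sets no lower or upper limit on pain duration and states: "Traumatic pain caused by soft tissue damage, contusion or otherwise (excluding fracture), will be included". The Statistical methods section places the primary analysis on those consulting their GP for the first time about the current pain.

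Time since onset is asked in Appendix 1, item 11 ("How long have you had your current pain"), with an open line and no unit. It does not appear in the Exposures list. The introduction reports from adult reviews that poor prognosis went with "higher pain severity upon presentation to the GP, longer pain duration, multiple-site pain" and other factors, and for the knee with symptoms lasting more than three months.

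**The concern.** A child seen two days after a sprain is eligible and can fall in the primary analysis. That child has no usual episode length, because the only episode has not ended, and no episode frequency. A child with months of unbroken pain has the same difficulty with item 14. Each must pick the nearest box, guess, or leave the item blank. The data will not show which of these happened, so later coding cannot fully undo it.

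New injury and long-standing pain may well differ in prognosis. If so, the odds ratios for two listed factors depend partly on which box these children choose. Time since onset is the variable that would separate the groups. It is collected in the least structured way on the form, from respondents as young as 8.

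**Working it through.** **Comparison of the places concerned.** The protocol states no figure on this point, so there is none to reproduce.

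1. Items 13 and 14 ask about episodes in general. Only item 13 uses the word usually, but item 14 also needs more than one episode to have a true answer.
2. The eligibility section admits pain of any duration and soft-tissue injury, so first and continuous pains are in scope.
3. Baseline item 14 has two answers and follow-up item 13 has three. The version that supplies the exposure is the one without the continuous-pain answer.
4. The baseline form provides for such cases elsewhere: the alcohol question has an answer for a single occasion, and the job question has one for having no job. Height, weight and daily sitting time have printed units. Item 11 has none.
5. Neither item 1 (first consultation or not) nor item 12 (cause) identifies a first episode. The telephone call after the form is retrieved is described only for checking eligibility.

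**Illustration for the frequency item.** All inputs are assumptions. Recurrent cases split 60/40 between weekly and less than weekly, with risks 0.60 and 0.4286. The odds are 1.50 and 0.75, so the true odds ratio is 2.0. First-episode children make up a share f of 10% to 40% and have risk 0.30.

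*All first-episode children tick less than weekly.* The risk in that group is [(1−f)·0.4·0.4286 + f·0.30] / [(1−f)·0.4 + f].
- f = 0.1: (0.1543 + 0.03)/0.46 = 0.4006, odds 0.668, OR = 1.50/0.668 = 2.24.
- f = 0.4: (0.1029 + 0.12)/0.64 = 0.3482, odds 0.534, OR = 2.81.

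*All tick weekly or more.* The risk in that group is [(1−f)·0.6·0.60 + f·0.30] / [(1−f)·0.6 + f].
- f = 0.1: (0.324 + 0.03)/0.64 = 0.5531, odds 1.238, OR = 1.238/0.75 = 1.65.
- f = 0.4: (0.216 + 0.12)/0.76 = 0.4421, odds 0.792, OR = 1.06.

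*They split 60/40 like the recurrent cases.*
- f = 0.1: risks 0.342/0.60 = 0.570 and 0.1663/0.40 = 0.4157, odds 1.326 and 0.711, OR = 1.86.
- f = 0.4: risks 0.288/0.60 = 0.480 and 0.1509/0.40 = 0.3771, odds 0.923 and 0.6055, OR = 1.52.

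The overall risk at f = 0.4 is 0.6·(0.6·0.60 + 0.4·0.4286) + 0.4·0.30 = 0.439. The protocol assumes 50%, so the upper end of the share range fits its planning figure less well. No comparable calculation was made for the duration item.

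**The case against.** - **The questions can be answered.** A child with three weeks of unbroken pain can tick over 7 days. The protocol says the wording was pilot tested in children of similar age and plans further piloting. This stands: a reader might infer that first-episode patients cannot answer, but the documents support only that their answers are ambiguous.
- **A first consultation is not a first episode.** A first-time consulter may have had recurrent pain for months, and the protocol gives no share of first-episode patients. This stands, and it rules out any claim about how many are affected.
- **Time since onset is collected.** Item 11 can be answered with a number and a unit and coded later, and coding can be left to the analysis plan. Table 1, said to hold the assessments, is not visible, and the Questionnaires section treats the questionnaire factors broadly as candidates. This also stands. A reader might infer that the study has no usable onset variable or has excluded it as a factor; neither can be shown.
- **The wide range of odds ratios needs every first-episode child to tick the same box.** This is correct. With the 60/40 split, the result is attenuation only.
- **Changing the items may reduce comparability with the cited studies.** This is a fair caution, met by adding answers and leaving the existing ones unchanged.

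None of this touches the central point. The answer options do not fit all eligible patients, the follow-up form already fills part of the gap, and an analysis plan cannot recover a category that the form did not offer.

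**Conclusion.** The point holds as a defect in the measurement of two listed exposures, worth correcting before the data are collected. Items 13 and 14 lack a first-pain answer, and item 14 also lacks the continuous-pain answer used at follow-up. Item 11 lacks a unit, and the Exposures list does not name time since onset.

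The direction and size of any bias are unknown. Under the assumed inputs, a frequency odds ratio of 2.0 would be seen as 1.86 to 1.52 with the 60/40 split, and within 1.06 to 2.81 at the extremes. These figures show that the problem can matter; they do not estimate its effect in this cohort. A reader might infer that both factors are bound to be biased. The documents do not support this, because it depends on a share of patients, their risk and their ticking behaviour, none of which is given.

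**What to change.** 1. Add to baseline items 13 and 14 an answer saying that this is the first time the child has had this pain.
2. Add to baseline item 14 the continuous-pain answer already in follow-up item 13, so that the two forms agree.
3. Print unit boxes on item 11 (days, weeks, months, years).
4. Name time since onset as a candidate factor if Table 1 does not already do so.
5. Code first episode once, as a single category or indicator shared by both items. Two separate indicators, if ticked consistently, would be identical and could not be estimated together. Keep all participants in the model and leave the existing categories intact for comparison with earlier studies.

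**Cost.** The edits are small but must be repeated in the Danish, Farsi and Arabic forms, with the planned translation checks. The model gains one or two parameters. The planned 480 participants at 50% with pain give 240 events, which is 12 variables at 20 events each. Adding one or two on top gives 240/13 = 18.5 or 240/14 = 17.1 events per variable, and the count stays within the stated 10 to 15 variables.

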The objective of this study is to investigate which descriptive patient variables (**exposures**) among 8-19-year-old children and adolescents with self-reported MSK pain (**population**), collected at time of recruitment, are associated to a higher risk of pain (**outcome**) at follow up.

FINER

F	Feasible	-Adequate no. of subjects: 500 -Technical expertise: N/A -Affordable in time and money: Time: short amount of time spent on recruitment per patient and recruitment executed by a GP employee or the GP. Money: a minimum cost per patient, according to rates by The Committee of Multipractice Studies in General Practice. -Manageable in scope: yes
I	Interesting	-Yes, high persistence of youth MSK pain and parental child pain acceptance
N	Novel	-Yes, lack of knowledge of prognostic factors in youth MSK pain and in the setting of general practice
E	Ethical	-Yes, approved by the National Ethics Committee (NVK)(28), without cause for further application.
R	Relevant	-To scientific knowledge: yes. -To clinical and health policy: yes. -To future research: yes.

Methods

Literature search to inform this study

Before commencing the planning of this cohort study, we conducted a systematic literature search to see if other prospective studies had investigated the same research question or were planning to do so. None specifically investigated childhood or adolescent prognostic factors for MSK pain in a general practice setting, nor did any of the included studies find any treatment effect modifiers(14). The systematic review in mention, has now been completed and this cohort study is based on the findings from that review. The prognostic factors found in our review, sparsely covered ethnicity, race, parental income, and residence, which will be investigated in this study. We furthermore limit our patient group to 8-19 years in order to preserve focus on an age group for which only limited knowledge on prognostic factors is available.

Design

This study is a prospective cohort study. We will use the STROBE guideline to report our study findings(29). Below is an illustration of the time line for our study process (figure 1), inspired by the guidelines of Prognosis Research, made by the PROGRESS Group(30). For validation of the prognostic screening, we will use the Transparent Reporting of a multivariable prediction model for Individual Prognosis Or Diagnosis (TRIPOD) Statement(31) and The TRIPOD Explanation and Elaboration document(32) (Appendix 4).

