2. carrying your school bag to school

3. sitting on a school chair for a 45 min. lesson

4. standing in a queue for 10 min.

5. sitting up in bed from a lying position

6. bending down to put your socks on

7. standing up from an armchair at home

8. running fast to catch a bus

9. sport activities at school

11) Tired during the day (42, 45).

Sample-size

The sample-size in this study was determined using the two following rationales: 1) a sample-size large enough to test and replicate the analyses from previous studies on. Given the prior odds (0.5, 1, 2) of follow-up MSK pain for patients, using estimates for the prognostic factors female sex, high disability index, multisite pain, and maximum HFAQ from our systematic review(14). We gained an estimate of P-values according to sample size, for all factors individually (Appendix 8). Sample size of 500 patients, would result in an estimate of P-values below 0.05 for all prognostic factors and 2) investigate a range of new prognostic factors related to the sparsely investigated ethnicity and socioeconomic status. As no one has yet tested any of these potential important prognostic factors, and never in a general practice setting, we decided on 500 subjects. The 500 subjects was decided based on 250 cases (we assume 50% will continue to experience pain at our primary follow-up time) giving approximately 125 cases per prognostic factor (500/number of prognostic factors). The results from this analysis will be considered as explorative as no studies have previously been conducted in a general practice setting. Again, assuming 50% has pain at follow-up and 20 events for each to be tested factor are needed. The model should allow for 10-15 variables in a multivariable logistic regression analysis. This would lead to a sample size of 480. Assumed, 5% is lost to follow-up and we have a sample-size of 504 included participants. Given the high prevalence of MSK pain at follow-up, this sample-size is feasible to include.

Questionnaires

We use three questionnaires in data collection of patient and parent characteristics: participant baseline questionnaire (Part-Quest-base) (Appendix 1), participant follow-up questionnaire (Part-Quest-follow-up) (Appendix 2), and the parent questionnaire (Pare-Quest) (Appendix 3).

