Appendix 3: Parent Questionnaire (Pare-Quest)

1. What is your relation to the child? (58)
 - Mother
 - Father
 - Other
2. What is your biological relation to your child?
 - Biological parent
 - Stepparent
 - Adoptive parent
3. How old are you? _____
4. What are your living arrangements with your child?
 - My child does not live with me
 - My child lives with me part time
 - my child lives with me full time
5. What is your relationship status with your child's other parent?
 - I am married to my child's other parent
 - I live with my child's other parent outside marriage
 - I am separated/divorced from my child's other parent/we don't live together
6. Where were you born? (58)
 - Denmark
 - Other – where? _____ and how many months/years have you lived in Denmark? _____
7. Do you smoke cigarettes? yes / no
8. Have you experienced chronic pain of more than 6 months, associated with arthritis, migraine, cancer, stomach ulcers or in your muscles, bones or tendons? (59) yes / no
9. Has one or more of your child's siblings had pain in their muscle, joint, bone or tendon? yes / no
10. Do you take pain killers, when you feel pain? yes / no
11. What do you feel the most as?
 - Danish
 - Danish with foreign background
 - Foreigner
12. Are you religious?
 - Yes
 - No
 - I don't know
13. What is your profession? _____ and how many hours do you work on a weekly basis? _____
14. How many years of education have you had? (58)
 - < 10 years
 - High school or other 10-12 years
 - Bachelor or other 13-15 years
 - University or other 15-17 years_
 - PhD or other > 18 years
15. What is the total income of your household b. tax? (58)
 - <200.000DKR
 - 200.000-350.000DKR
 - 350.000-750.000DKR
 - >750.000DKR
16. Has a health care professional ever given your child the diagnosis hypermobility? yes / no
17. Does your child have a measured/known vitamin D insufficiency? yes / no
18. Has your child been vaccinated (once or more) against HPV (Human Papilloma Virus)? yes / no
19. Has your child received physiotherapy in the past 6 months for the current pain condition? yes / no
20. Do you believe your child feels anxious or depressed? yes / no
21. Do you believe your child has low self-esteem? yes / no
22. Have you accepted your child's pain condition? yes / no
23. Would you like the general practitioner to give your child pain medication? yes / no
24. Why did your child visit the doctor with his/her pain condition? You may circle more than one answer.
 - For pain relief

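### Baseline item 17 has no Denmark option, so a blank can mean either Danish birth or non-response; the effect is minor and one tick box removes it

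*Protocol*

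**What the plan says.** Protocol, Appendix 1, item 17 reads "If not born in Denmark, in which country were you born and how long have you lived in Denmark", and its only response fields are "Country of birth _____ Months/years lived in Denmark" with a blank after each. The next item, on what the child feels most as, is put to everyone: "Please answer this question, no matter country of birth".

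Appendix 3 (parent form), item 6 asks the parent "Where were you born? (58" (the trailing figure is a reference marker) and offers Denmark or another country to be named. It concerns the parent's birth, not the child's.

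Ethnicity is a declared interest of the study. The literature-search part of Methods says that the earlier review's factors "sparsely covered ethnicity, race, parental income, and residence, which will be investigated in this study". The Sample-size section gives as its second rationale to "investigate a range of new prognostic factors related to the sparsely investigated ethnicity and socioeconomic status", and calls the results of that analysis explorative.

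**The concern.** A conditional question with no box for the common answer gives a blank two meanings: the child was born in Denmark, or the child did not answer. Other baseline items avoid this. Item 5 asks for a mark if there was no pain, and the painkiller and job items each carry an explicit negative. Under Statistical methods, the protocol also presents asking Danes and non-Danes the same identity question as a safeguard against information bias. Item 17 departs from that practice.

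At stake is the quality of one ethnicity-related exposure. Foreign-born children who skip the item cannot be separated from Danish-born children, their length of residence is lost in the same blank, and the number of missing answers cannot be counted. A later analysis plan can choose how to code a blank, but it cannot supply an answer that the form did not collect.

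**Working it through.** **Can the child's birthplace be found elsewhere?**

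- Appendix 1, item 18: asks how the child feels and includes a don't-know option. It does not ask birthplace.
- Appendix 1, item 19: asks about friends' background.
- Appendix 2 (follow-up form): does not ask birthplace again.
- Appendix 3, items 6 and 11: the parent's birthplace and the parent's identity. Under Recruitment of parents, a parent may decline while the child stays in.
- Phone call under the eligibility criteria: "During a phone call made by the research assistant to either the participant or her/his parent, after retrieving their completed questionnaire from the GP clinic". It is listed as a time-point for applying inclusion and exclusion criteria. Completing blank items is not mentioned.

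No shown item asks it.

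**How would a blank be coded?** The protocol gives no rule. If blanks were set to missing, nearly all Danish-born children would drop out of the variable. A usable variable therefore has to read blanks as Danish-born. This is an inference from the form, not a statement in the protocol.

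**How large could the effect be?** The documents give no figure for this point, so what follows is an illustration. The only input from the protocol is the number of children: "This would lead to a sample size of 480". That figure reproduces with 12 variables: 12 × 20 / 0.50 = 480, and 480 × 1.05 = 504. The finding does not depend on it.

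Assumptions, none in the documents: foreign-born share π = 5-20%; skipping among them s = 10-50%, unrelated to outcome; risk of pain 0.50 in the Danish-born; true odds ratio 2.0, hence risk 2/3 in the foreign-born; blanks read as Danish-born.

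Formulas:
- Misfiled = 480·π·s
- Contamination of the reference group c = πs / (1 − π + πs)
- Apparent reference risk r = 0.5(1 − c) + (2/3)c
- Observed OR = 2 / [r/(1 − r)]
- SE of log OR = √[1/(n₁·(2/3)(1/3)) + 1/(n₀·r(1 − r))], where n₁ and n₀ are the group sizes as coded

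Worked case, π = 10%, s = 30%: 48 foreign-born, 14.4 misfiled, 33.6 left. c = 14.4/446.4 = 0.0323; r = 0.5054; OR = 2/1.0217 = 1.957. The SE with all answers is √(1/10.67 + 1/108) = 0.321. The SE as coded is √(1/7.47 + 1/111.6) = 0.378.

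| Share | Skip | Misfiled | Left in exposed group | c | Observed OR | SE, all answers → as coded |
|---|---|---|---|---|---|---|
| 5% | 10% | 2.4 | 21.6 | 0.5% | 1.993 | 0.443 → 0.466 |
| 5% | 50% | 12.0 | 12.0 | 2.6% | 1.966 | 0.443 → 0.619 |
| 10% | 30% | 14.4 | 33.6 | 3.2% | 1.957 | 0.321 → 0.378 |
| 20% | 50% | 48.0 | 48.0 | 11.1% | 1.857 | 0.239 → 0.321 |

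Attenuation is small throughout. The larger cost is the thinner exposed group. That part comes from the skipping itself: in the worked case, leaving the skippers out as missing gives √(1/7.47 + 1/108) = 0.378 as well. Making the blank visible removes the attenuation. Precision is recovered only if the visible blanks are then queried.

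**The case against.** The strongest reply is that little hangs on item 17. The ethnicity item that the protocol discusses at length is item 18, which goes to every child with full response options. Friends' background, the parent's birthplace and the parent's identity are collected as well, and no section makes the child's own birthplace the analysed ethnicity variable. This stands, and it limits the weight of the point.

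A reader might infer that the protocol itself codes every missing answer as the reference category. It does not: no coding rule or reference category is given, and the analysis plan is to be finalised before the last patient is enrolled. What stands is narrower. The plan can choose a rule, but no rule separates the two meanings of a blank.

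A reader might also infer that skipping is concentrated among children with weak Danish. The Translation of questionnaires section does expect such participants, but it also provides professional translation into Farsi and Arabic, and pilot testing is planned. Nothing in the documents shows differential skipping.

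Nor are blanks strictly beyond recovery. Item 18 or a foreign-born parent could flag forms worth querying, contact details are on the form, and participants are phoned. The first call is stated for eligibility and the later ones as reminders, so the route exists but the protocol does not assign it this use.

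**Conclusion.** The point holds as a minor defect of the form. A blank in item 17 is ambiguous, no other item asks the child's birthplace, and under the only coding that leaves a usable variable, foreign-born skippers join the Danish-born. The item's missing rate then cannot be determined.

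Under the stated assumptions an odds ratio of 2.0 moves to between 1.99 and 1.86, with a loss of precision that becomes marked only at the highest skip rates. The shares and skip rates are assumed. If skipping were related to outcome, the bias could be larger, but the documents give no reason to suppose so.

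Three stronger readings are not supported. Danish-born children who leave the item blank are not misclassified; they only hide the missing rate. An uncountable missing rate for one item is not a failed reporting requirement, since the Design section names STROBE for the study findings and TRIPOD for validating the prognostic screening. And the ethnicity aim as a whole is not undermined. The primary outcome and sample size are untouched.

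**What to change.** Replace item 17 with: *In which country were you born? [ ] Denmark [ ] Other: ____, lived in Denmark for ____ months/years.* This is the format of parent item 6. State that a form with neither box marked counts as missing for birthplace.

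The cost is one tick box, carried into the translated versions, with no real added burden for the child. If forms are already in use, ask birthplace once in the existing phone call after the baseline form is retrieved, or add the question to the first follow-up form. Either would settle blanks already returned, for the children who are reached.
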